#### **Exclusion Criteria:**

- 1. Subject with a BMI ≥ 65
- 2. Subject is medically unable to consent (due to head trauma, coma, etc.) or cognitively impaired (due to being mentally challenged, having Alzheimer's, etc.)
- 3. Subject is an active smoker
- 4. Subject has any history of fish allergy or a known sensitivity to any of the SOC materials which come into contact with the skin
- 5. Ankle-Branchial Index (ABI) less than 0.80 or greater than 1.3
- 6. Presence of any monophasic waveforms
- 7. Subject has the following abnormal lab values: Albumin < 2.5 g/dL; Total Protein < 5 g/dL; BUN above 25 mg/dL; Creatinine > 3.0 mg/dL
- Any active cancer other than a nonmelanoma skin cancer; any previous cancer must be in remission for at least 1 year; bone cancer or metastatic disease of the affected limb, radiation therapy to the foot, or has had chemotherapy within the last 12 months
- 9. Suspicion of malignancy within VLU. Any wound that has been present for ≥ 6 months and hasn't previously been biopsied, a biopsy must be performed. Also, if a clinical suspicion of malignancy exists in the opinion of the Investigator, a biopsy should be performed regardless of duration of wound
- 10. Life expectancy < 6 months
- 11. Subject has received within 28 days of screening a treatment which is known to interfere with or affect the rate and quality of wound healing (e.g., thrombolysis, systemic steroids, immunosuppressive therapy, autoimmune disease therapy, dialysis, radiation therapy, chemotherapy) to the leg or who may receive such medications during the screening period or who are anticipated to require such medications during the course of the study.
- 12. History of immunodeficiency or any illness or condition that could interfere with wound healing e.g., lymphedema, end-stage renal disease, severe malnutrition, liver disease, aplastic anemia, Raynaud's Syndrome, connective tissue disorder, acquired immune deficiency syndrome, HIV positive, or sickle cell anemia
- 13. Ulcers due to non-venous etiology and leg ulcers associated with mixed etiology
- 14. Untreated osteomyelitis
- 15. Hepatitis
- 16. Acute deep venous thrombosis
- 17. Allergy to lidocaine and/or epinephrine
- 18. Subject's inability to successfully tolerate compression therapy that is changed weekly
- 19. Suspected or confirmed gangrene or wound infection of the study ulcer, as evidenced by tissue necrosis, redness, pain, and/or purulent drainage and/or receiving systemic antibiotics for the treatment of such
- 20. Target wound has received hyperbaric therapy or wound dressings that include growth factors, engineered tissues, or skin substitutes within 28 days of randomization or is scheduled to receive treatment during the study e.g., Apligraf, PriMatrix, AMNIOEXCEL (first generation), Regranex, Dermagraft, EpiFix, GraftJacket, OASIS, Omnigraft, or Integra BMWD

#### Eligibility Criteria Diabetic Foot Ulcer (DFU):

#### **Inclusion Criteria:**

- 1. Male or female 21-80 years of age
- 2. Participated in the informed consent process and signed study specific informed consent document
- 3. Willing and able to comply with study procedures, including study visits and study dressing regimens
- 4. Diagnosed as having Type 1 or Type 2 diabetes
- 5. HbA1c of ≤ 10%
- 6. Presence of a DFU, Wagner 1 or 2 (see **Appendix 7** for definitions), extending at least through the dermis provided it is below the level of the medial or lateral malleolus. Any wound that has been present for ≥ 6 months and hasn't previously been biopsied, a biopsy must be performed to exclude other skin conditions e.g. cancer for ulcers. Also, if a clinical suspicion of malignancy exists in the opinion of the Investigator, a biopsy should be performed regardless of duration of wound
- 7. Target wound will be located on the foot or ankle and will be the largest ulcer if two or more DFUs are present with the same Wagner grade and will be the only one evaluated in the study. If other ulcerations are present on the same foot, they must be more than 1 cm distant from the target wound
- 8. Target wound (i.e. current episode of ulceration) has been present for greater than 4 weeks prior to screening visit and less than 12 months, as of the date the subject consents for study
- 9. Target wound size ≥0.25 cm² to ≤ 150 cm² post debridement at Screening Visit and Treatment Visit Week 1/Randomization

#### **Exclusion Criteria:**

- 1. Subject with a BMI ≥ 65
- 2. Subject is medically unable to consent (due to head trauma, coma, etc.) or cognitively impaired (due to being mentally challenged, having Alzheimer's, etc.)
- 3. Subject is an active smoker
- 4. Subject has any history of fish allergy or a known sensitivity to any of the SOC materials which come into contact with the skin
- 5. Target wound(s) deemed by the investigator to be caused by a medical condition other than diabetes or subject has wounds secondary to a disease other than diabetes (e.g. vasculitis, neoplasms, or hematological disorders)
- 6. Ankle-Branchial Index (ABI) less than 0.80 or greater than 1.3
- 7. Presence of any monophasic waveforms
- 8. Subject has the following abnormal lab values: Albumin < 2.5 g/dL; Total Protein < 5 g/dL; BUN above 25 mg/dL; Creatinine > 3.0 mg/dL
- Subject is unable to safely ambulate with the use of a study required offloading method
- 10. Any active cancer other than a nonmelanoma skin cancer; any previous cancer must be in remission for at least 1 year; bone cancer or metastatic disease of the

affected limb, radiation therapy to the foot, or has had chemotherapy within the last 12 months

- 11. Subject has received within 28 days of screening a treatment which is known to interfere with or affect the rate and quality of wound healing (e.g., thrombolysis, systemic steroids, immunosuppressive therapy, autoimmune disease therapy, dialysis, radiation therapy, chemotherapy) to the foot or during the screening period or who are anticipated to require such medications during the course of the study
- 12. Subject on any investigational drug(s) or therapeutic device(s) within 28 days preceding randomization
- 13. History of radiation at the ulcer site (regardless of time since last radiation treatment)
- 14. Target wound has received or hyperbaric therapy or wound dressings that include growth factors, engineered tissues, or skin substitutes within 28 days of randomization or is scheduled to receive treatment during the study (e.g., Apligraf, PriMatrix, AMNIOEXCEL (first generation), Regranex, Dermagraft, EpiFix, GraftJacket, OASIS, Omnigraft, or Integra BMWD)
- 15. Presence of any condition(s) which seriously compromises the subject's ability to complete this study or has a known history of poor adherence with medical treatment
- 16. Osteomyelitis or bone infection of the affected foot as verified by x-ray within 30 days prior to randomization. (In the event of an ambiguous diagnosis, the subject will not be enrolled)
- 17. Suspected or confirmed gangrene or wound infection of the study ulcer, as evidenced by tissue necrosis, redness, pain, and/or purulent drainage and/or receiving systemic antibiotics for the treatment of such
- 18. History of immunodeficiency or any illness or condition, other than diabetes, that could interfere with wound healing e.g., excessive lymphedema, end-stage renal disease, severe malnutrition, liver disease, aplastic anemia, Raynaud's Syndrome, connective tissue disorder, acquired immune deficiency syndrome, HIV positive, or sickle cell anemia
- Subject has unstable Charcot foot or Charcot with bone exposed that could inhibit wound healing

### 4.3 Subject Identification and Randomization

### 4.3.1 **Subject Identification**

At the Screening Visit, a unique 5-digit subject number will be assigned consecutively for each subject after he or she signs the Informed Consent Form (ICF). Unique subject numbers will begin with the clinical site number, e.g., 01 followed by a 3-digit number starting with 001. For example, for clinical site number 02, the unique subject numbers will be as follows: 02-001, 02-002, 02-003, etc.

#### 4.3.2 Randomization Scheme

It will be determined if a subject is eligible to participate in the study at Treatment Visit Week 1, and the subject will be randomized 2:1 to Omeza® Products Bundle or SOC. Randomization numbers will be generated in blocks and consist of the 2-digit site number, followed by a 4-digit subject number. Randomization numbers will be assigned consecutively to each subject in the order in which they become eligible for randomization. Since this is an open label study, a randomization schedule indicating if the subject is assigned to TEST or SOC will be provided to each study site.

The subject will keep this unique randomization number for the duration of the study. Once a subject is randomized, the randomization number will be the identifying number for that subject.

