#### indication).

Subjects who are diagnosed with one of the following chronic ulcers and who meet the entry criteria will be randomized into the study: 1) venous leg ulcer or 2) diabetic foot ulcer

Each indication will require 26 TEST subjects and 13 SOC control subjects assigned for a combined total of 78 randomized subjects.

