#### 4.3.3 **Subject Withdrawal**

It is planned to randomize approximately 78 subjects, with 39 subjects per indication (VLU or DFU), at up to 3 clinical sites for this study. See **Section 10.4**, for a discussion of sample size. Pls may choose to discontinue a subject's participation in the study if they believe it is in the subject's best interest clinically. The reason(s) for withdrawal must be recorded on the eCRF. If a subject is prematurely withdrawn from the study for any reason, the PI must make every effort (with proper documentation) to perform the evaluations described for the End of Study Visit. A subject may also be withdrawn from study by the sponsor or the IRB. Subjects who fail to qualify for enrollment during Screening Period will be considered Screen Failures and the reason for failure will be documented.

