# 10 Statistical Considerations (See Statistical Analysis Plan [SAP])

### 10.1 General Considerations and Populations

The primary endpoint is percent change from baseline in target wound measure by Week 12/End of Study.

All statistical testing will be performed at a two-sided alpha=0.05 level of significance. A detailed Statistical Analysis Plan (SAP) will be finalized prior to database lock.

All subjects who are randomized and receive at least one study treatment will be included in the Safety Population. All summaries of safety data will be based on this population and reported "as treated" – in case there are subjects that were not treated as per the randomization outcome.

All subjects who are randomized, receive at least one study treatment and have at least one post-baseline measure assessment will be included in the Intent-to-Treat Population (ITT). All efficacy summaries will be based on this population and will be reported according to the intent to treat principle (as randomized).

A review of major protocol violations will be performed. Major violations will include, but not be limited to, an assessment of compliance, use of concomitant medications and intercurrent illnesses. Subjects and data points without major protocol violations will be included as part of the Per-Protocol Population. If fewer than 10% of the subjects have major protocol violations, these analyses may not be performed.

All analyses and summaries will be reported overall and for each indication (venous leg ulcers and diabetic foot ulcers).

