## 10.4 Sample Size Rationale

The power of the study is computed for the primary endpoint of "percent change from baseline in target wound measure by Week 12" comparing the two means. The combined sample size of 78 subjects (randomized 2:1) will provide over 80% power to detect a difference of about 14 units (percent change from baseline in wound measure by Week 12), assuming a standard deviation of 20 units, and a 2-sided significance level of 5%.

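### Section 4.3.2 names no stratification by ulcer type, so the 26/13 split required in each indication is not ensured, and the pooled primary model does not adjust for ulcer type

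*Protocol*

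**What the plan says.** The synopsis (Number of Subjects and Population) fixes the allocation within each ulcer type: "Each indication will require 26 TEST subjects and 13 SOC control subjects assigned for a combined total of 78 randomized subjects". Section 4.3.3 repeats the total less firmly: "It is planned to randomize approximately 78 subjects, with 39 subjects per indication (VLU or DFU), at up to 3 clinical sites for this study".

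Section 4.3.2 describes the mechanism. At Treatment Visit Week 1 eligibility is settled, "and the subject will be randomized 2:1 to" the bundle or SOC, and the numbers are built as follows: "Randomization numbers will be generated in blocks and consist of the 2-digit site number, followed by a 4-digit subject number". On order of use: "Randomization numbers will be assigned consecutively to each subject in the order in which they become eligible for randomization". On the list itself: "a randomization schedule indicating if the subject is assigned to TEST or SOC will be provided to each study site". Neither block size nor stratification factors are given, and indication does not appear in the number, the list or the order of assignment.

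On analysis, Section 10.1 states: "All analyses and summaries will be reported overall and for each indication (venous leg ulcers and diabetic foot ulcers". Section 10.2 specifies the primary MMRM with treatment and visit as fixed effects and subject as a random effect. Indication and site are not among the terms. Section 10.4 bases power on the pooled 78 subjects only.

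**The concern.** The synopsis sets an allocation target inside each indication, but the section that should deliver it never mentions indication. Read literally, a VLU subject and a DFU subject at one site take the next number from the same sequence. The overall ratio is then held near 2:1, but the ratio within each ulcer type is left to chance.

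Two things follow. First, the SOC group in an indication is meant to be only 13, and it can come out smaller. Second, the powered analysis pools both ulcer types and, as specified, does not adjust for type. The entry criteria in Section 4.2 differ: VLU must be at least 4 cm² and 3 to 12 months old, while DFU may be as small as 0.25 cm² and need only be more than 4 weeks old. Background care differs too (compression against offloading). A difference in mean percent change between the types is therefore plausible, although the protocol does not quantify one. If it exists, an uneven mix of types between the arms moves the pooled estimate.

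**Working it through.** **Inputs from the protocol.** 78 subjects, 2:1, so 52 TEST and 26 SOC; 39 per indication; up to 3 sites (Synopsis, Sections 4.3.2 and 4.3.3). Difference 14, SD 20, two-sided 5% (Section 10.4). **Assumed, because the protocol is silent:** a list that ignores ulcer type; block sizes of 3 or 6; site sizes and case-mix; the difference D between ulcer types in mean percent change, taken as 10, 20 or 30 units.

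**1. The plan's own power.** SE = 20 × √(1/52 + 1/26) = 4.80. The ratio 14/4.80 = 2.91 gives power 0.83 (normal) or 0.82 (noncentral t, 76 df). The stated "will provide over 80% power to detect a difference of about 14 units" is reproduced.

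**2. How often 26/13 occurs.** If the list ignores ulcer type, the SOC count among the 39 subjects of one indication is hypergeometric (78 subjects, 26 SOC, 39 drawn). The mean is 13 and the variance is 39 × (1/3) × (2/3) × (39/77) = 4.39, so the SD is 2.1.

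| Departure from 13 SOC | Probability |
|---|---|
| 0 (exactly 26/13 in both indications) | 0.19 |
| 2 or more | 0.47 |
| 3 or more (one indication has 10 or fewer SOC) | 0.23 |
| 4 or more | 0.09 |

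Simulation of permuted blocks of 3 or 6 within three sites (20,000 runs per scenario) gave an exact split in both indications in 7% to 19% of runs with similar case-mix across sites, and in 11% to 25% with strongly different case-mix. The mean difference between arms in VLU share was essentially zero throughout.

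**3. Shift of the pooled difference in one realized trial.** Shift = (VLU share in TEST − VLU share in SOC) × D. Take VLU at 29/10 and DFU at 23/16, a departure of 3. The shares are 29/52 = 0.558 and 10/26 = 0.385, a difference of 0.173. The imbalance can equally run the other way.

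| Imbalance | Share difference | D = 10 | D = 20 | D = 30 |
|---|---|---|---|---|
| Off by 2 (28/11) | 0.115 | 1.2 | 2.3 | 3.5 |
| Off by 3 (29/10) | 0.173 | 1.7 | 3.5 | 5.2 |
| Off by 4 (30/9) | 0.231 | 2.3 | 4.6 | 6.9 |

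For an imbalance of 3 the shift is 1.7/4.8 = 0.4, 3.5/4.8 = 0.7 or 5.2/4.8 = 1.1 standard errors, and 12%, 25% or 37% of the 14-unit target. If D = 0 there is no shift.

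**4. Precision.** One subject of departure changes the share difference by 1/52 + 1/26 = 0.058, so its SD over repeated randomizations is 0.058 × 2.1 = 0.12. The shift then has an SD of about 1.2, 2.4 or 3.6 units for D = 10, 20 or 30. An unadjusted analysis carries this as noise.

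**5. Within an indication.** For 14 units and SD 20, power (noncentral t) is 52% at 26/13 and 46% at 29/10.

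**6. After the change.** 39 = 13 × 3. A central list for each indication, in blocks that fill 39, gives exactly 26/13 in each. The share difference and the shift are both 0, and pooled power stays at 0.82 to 0.83.

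**The case against.** A reader might infer that randomization is stratified by site alone. The protocol does not say so. The inference rests on the site prefix, the schedule given to each site and the consecutive assignment, and all three are compatible with a schedule that has separate VLU and DFU sections. The 26/13 requirement is itself what such lists would produce. This stands: an undescribed stratified list cannot be excluded, and every probability above is conditional on its absence. But then Section 4.3.2 omits the feature that makes the synopsis true, and the same sentence is needed.

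A reader might also infer that the scheme cannot produce 26/13. It can, about one time in five, and Section 4.3.3 plans only approximately 78 subjects. What the scheme does is fail to ensure the split.

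The strongest temptation is to call the pooled comparison confounded or biased. Neither word fits. The imbalance is due to chance and has expectation zero, so the unadjusted estimate is unbiased over repeated randomizations. If the planning SD of 20 describes the mixed population, it already contains the variation between types. The 29/10 example is also a departure of about 1.4 SD, not a typical one, and no value of D is documented, which is why a range is shown.

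Two further points have force. The analyses by indication cannot be distorted by ulcer type, and the fall in their power from 52% to 46% is modest. The low power at exactly 26/13 is a separate matter. Finally, an SAP that is not at hand might add an indication term. Section 10.2 nevertheless lists the model terms, and indication is not among them.

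**Conclusion.** The point holds as a gap between a stated allocation requirement and the scheme meant to meet it. As written, Section 4.3.2 does not ensure 26/13 in each indication, and the pooled primary model does not adjust for ulcer type.

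If the list ignores ulcer type, the exact split is missed in roughly four trials in five (75% to 93% across the assumed block sizes and case-mix), and one indication has 10 or fewer SOC subjects in about 23%. For the pooled estimate the consequence is an uncorrected shift in the realized trial, usually below one standard error, together with some loss of precision. Both vanish if the ulcer types have the same mean percent change. This does not invalidate the trial. It is worth changing because a design and analysis factor already known at randomization is left unused, and allocation cannot be repaired after enrollment.

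**What to change.** In Section 4.3.2, state that the blocked 2:1 allocation is stratified by indication, with separate VLU and DFU lists each capped at 39. If such lists already exist, describe them. In Section 10.2, add indication as a fixed factor in the pooled MMRM, and use it as the stratum in the pooled comparisons of time to closure and proportion healed.

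The cost is one extra list and one model term, using a variable collected on every subject. There is one trade-off. Keeping the schedules at site level means up to 3 × 2 = 6 lists, a few of which will end in incomplete blocks, so the synopsis should then describe 26/13 as approximate. Guaranteeing it exactly would need central lists in place of the per-site schedule, which is a larger operational change and not necessary for this purpose.

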### 3 Study Design

### 3.1 Description of the Study Design

This is a randomized, multicenter, open-label study comparing the Omeza® Products Bundle versus standard of care treatments for 2 different types of chronic ulcers (venous leg ulcers and diabetic foot ulcers). The treatment period will be 12 weeks, with subjects coming into the study site weekly for evaluations, photography and formal measurements of the target wound, and dressing changes. There will be a total of 13 study site visits. The Screening Visit (Day 0) will occur 1 week prior to randomization and will include routine labs and vascular assessment to determine inclusion/exclusion of the potential subject from the study; followed by weekly treatment visits (Week 1 through Week 11); randomization will occur at Treatment Visit Week 1; the Treatment Visit Week 12/End of Study Visit will include end of study labs. Target wounds will be photographed and measured, and vascular assessment will be done at each of the 13 visits. Standard of care will be billed to subject's insurance for both TEST and SOC.

If the wound closes before Week 12, the subject will continue to come in for all the remaining study visits until study completion. If the wound does not close by Week 12, the subject will be immediately exited from the study and no further follow-up will occur as part of the study.

Table 1: Study Plan

Study Period	Visit	Purpose
Screening	Screening (Day 0)	Determine eligibility, routine labs,
		vascular assessment, photos and
		measures
Baseline /	Treatment Visit Week 1	Review eligibility, randomization,
Randomization		Wound-QoL questionnaire, vascular
		assessment, photos and measures,
		begin study treatments.
Treatment	Treatment Visits Week 2 - Week	Study treatments, vascular assessment,
	11	photos and measures
End of Study Visit	Treatment Visit Week 12	End of Study routine labs, vascular
		assessment, photos and measures,
		Wound-QoL questionnaire

For subject to be eligible they must meet entry criteria. If the subject is not found eligible at Treatment Visit Week 1, the subject may be re-screened once or may be replaced.

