### 5.4 Dosage and Administration of Study Agent

At each treatment visit (Weeks 1 through Week 12), each subject will undergo the wound care procedure as outline in the assigned randomized treatment i.e. either the Omeza® Products Bundle (TEST) or the standard of care (SOC). In all cases each treatment will be applied according to the diagnosed indication. If the wound closes before Week 12, the subject will continue to come in for all the remaining study visits until study completion, but the TEST subjects will be treated with the Omeza® Skin Protectant only.

The TEST treatment will be labeled with a subject's unique randomization number, (which is also the kit number). In addition, the visit number will be hand-written on the label at the site. The adhesive label will be placed on the subject's chart (source) and documented in the eCRF.

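### Giving each site the TEST/SOC randomization schedule removes allocation concealment: whoever confirms eligibility can know the next arm, so selection bias is possible

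*Protocol*

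**What the plan says.** Protocol section 4.3.2 (Randomization Scheme) fixes four things:

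- **Who receives the list.** "a randomization schedule indicating if the subject is assigned to TEST or SOC will be provided to each study site". The reason given is "Since this is an open label study".
- **How the list is built.** "Randomization numbers will be generated in blocks and consist of the 2-digit site number, followed by a 4-digit subject number". Block size is not stated.
- **How it is used.** "Randomization numbers will be assigned consecutively to each subject in the order in which they become eligible for randomization".
- **When eligibility is settled.** "It will be determined if a subject is eligible to participate in the study at Treatment Visit Week 1", which is also the randomization visit (section 6.2).

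Section 3.1 adds: "If the subject is not found eligible at Treatment Visit Week 1, the subject may be re-screened once or may be replaced".

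Section 5.4 ties the TEST kit to the list: the kit carries the subject's "unique randomization number, (which is also the kit number").

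Nowhere does the protocol describe central or interactive release, sealed envelopes, a list holder independent of the site, or a rule that eligibility must be locked before the schedule is consulted.

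**The concern.** Blinding and allocation concealment are separate protections. An open-label trial gives up the first, but it can and should keep the second, which lasts only until the subject is assigned. The protocol treats the loss of one as a reason to give up the other.

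A schedule used in strict order and held at the site shows what the next eligible subject will receive. Some entry criteria leave room for judgement: suspected wound infection in both indications, a history of poor adherence in the DFU list, and inability to tolerate compression in the VLU list. Someone who can see the next arm can apply these more or less strictly, or defer a subject through the re-screening allowance.

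The arms could then differ in prognosis at entry. The primary model in section 10.2 has treatment, visit and a random subject effect, and names no baseline covariate. Even an adjusted model could not recover selection on unmeasured features. With at most 3 sites and 26 SOC subjects in total, a few steered subjects could move an arm mean. The harm cannot be undone after enrolment, and this is a matter of conduct that an analysis plan would not be expected to resolve.

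**Working it through.** **1. Can the next arm be known?** Taking the provisions of sections 4.3.2 and 3.1 together:

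- The site holds a schedule showing the arm.
- Entries are used in order, so the next one is always identifiable.
- The last eligibility decision falls at the visit at which the entry is used.
- A subject not found eligible then "the subject may be re-screened once or may be replaced".
- No step separates the holder of the schedule from the assessor of eligibility.

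The next arm is therefore knowable to the assessor. If the whole schedule is supplied in advance and consulted, every assignment is foreseeable. That is the upper limit.

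**2. The plan's own power figure.** Inputs from section 10.4: 78 subjects at 2:1 (52 TEST, 26 SOC), SD 20, difference 14, two-sided 5%.

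- SE = 20 × √(1/52 + 1/26) = 4.80
- Noncentrality = 14 / 4.80 = 2.91
- Power = 82.1% (noncentral t, 76 df) or 83.0% (normal approximation)

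The stated power of over 80% is reproduced, and this point does not change it.

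**3. Illustration of what a bias would do.** Let b be the prognostic difference between arms caused by foreknowledge, in percent-change units, with no true treatment effect. The protocol gives no value for b, so a range is assumed. The rejection probability is P(|T| > 1.992), where T is noncentral t with 76 df and noncentrality b / 4.80.

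| Assumed b | b / SE | False-positive rate (t) | Normal approximation |
|---|---|---|---|
| 0 | 0 | 5.0% | 5.0% |
| 2 | 0.42 | 7.0% | 7.0% |
| 4 | 0.83 | 13.0% | 13.2% |
| 6 | 1.25 | 23.4% | 23.9% |

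One way to reach b = 4: good- and poor-prognosis subjects differ by 20 points, and the good-prognosis share differs by 20 percentage points between arms, so 20 × 0.20 = 4. That is 4 / 14 = 29% of the target difference. Both inputs are assumptions.

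**4. Why block sizes matter once the list is withdrawn.** Past assignments stay visible in an open-label trial. Suppose sites knew that blocks were fixed at 3 (an assumed size). The three possible orders at 2:1 contain 2, 1 and 1 assignments that are certain from those before them, so 4 of 9 = 44%. For fixed blocks of 6 (also assumed), enumerating the 15 orders gives 26 of 90 = 29%.

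**The case against.** **The text does not say that the assessor knows the next arm.** It names no holder of the schedule within the site and does not describe the entries as upcoming. This stands. A reader might infer that whoever confirms eligibility does see the next assignment; the document supports only that this person can, because nothing prevents it.

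**The room for steering is limited.** Entry criteria are reviewed, and labs and vascular assessment done, at Screening a week earlier (section 6.1). Many criteria are objective: ABI, HbA1c, albumin, creatinine, wound area and duration. Randomized subjects are not replaced (section 9.8), and reasons for screen failure are documented (section 4.3.3). This also stands, and it reduces the scope for selection and leaves some audit trail. It does not remove the scope, because criteria are reviewed again at Week 1 and some of them rest on judgement.

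**The kits might seem to reveal the sequence a second time,** since only TEST subjects have kits and the kit number is the randomization number. That holds only if kits arrive already numbered, which is not established. The sample label in section 5.2 shows a number field with no value, beside one for the subject's initials. Section 5.5 has the randomization number written on the label along with the initials, visit and date. Section 5.4 can be read either way. If the number goes on after randomization, the kits reveal nothing. The point does not rest on them.

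**The magnitude has no source in the protocol.** Agreed: the bias values and block sizes are assumptions. They show how sensitive the test would be and are not evidence that bias of that size will occur.

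**Conclusion.** The point holds. Following section 4.3.2 as written leaves the trial without allocation concealment, for a reason that does not justify it. Selection bias is possible; the document does not show that it will occur or how large it would be. On assumed imbalances of 2, 4 and 6 points, the false-positive rate would rise from 5% to about 7%, 13% and 23%. Those figures rest on the planned 52 and 26 subjects, the planned SD of 20 and no true effect.

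The conclusion depends on none of these numbers. It rests on the site-held schedule, consecutive use, eligibility confirmed at the randomization visit, and the absence of any barrier between schedule and assessor. It should be corrected in the protocol because randomization is the trial's main protection for a causal comparison and later analysis cannot restore it.

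**What to change.** In section 4.3.2, delete the sentence that provides the schedule to sites. In its place, state that:

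- the list is held centrally, for example at the CRO;
- each assignment is released singly, through the EDC system already planned in section 12.3 or through sequentially numbered opaque sealed envelopes;
- release happens only after Week 1 eligibility is signed off in the eCRF.

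Preferably, vary the block sizes and do not disclose them to sites.

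Clarify sections 5.2, 5.4 and 5.5 on when the randomization number goes onto the TEST kit. If kits would otherwise be numbered before shipment, have the number written on only after randomization. Separate kit numbering is not needed.

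The cost is a protocol wording change and the minor set-up of an EDC randomization form or envelopes. Sample size, visits and analysis are unchanged.
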